
This study represents a case of a forty-year-old woman who presented with a second-degree burn to her right abdominal flank obtained 7 weeks prior secondary to liposculpture. On admission her scar was scaled as an 11 on the Vancouver scar scale (VSS) and a 49 on the Patient scar assessment scale (PSAS). Treatments of autologous platelet-rich plasma with platelet concentrations between 300% and 400% were applied to the edges of the burn on days 0, 30, 60, 90, 120, and 180. Ten months out from initial presentation, the patient's VSS had dropped to 2 and her PSAS had dropped to 10. Most notably, her pain had dropped from an 8 on initial presentation to a 0. This case report, in combination with the study done in rats by Huang et al, leads us to believe that PRP may be a potential treatment for reducing neuropathic pain in burn scar patients. Our study will be the first to investigate pain outcomes in relation to treatment of burn scars with PRP.

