# 4. Inclusion/Exclusion Criteria

Inclusion Criteria:

- 18-70 years old, all sexes
- Thermal burn scar on the trunk or abdomen ≥ 1 year old that meets ONE of the following criteria:
  - Vancouver Scar Scale score  $\geq 7$
  - Patient and Observer Scar Assessment Scale (POSAS) score ≥ 35
  - Neuropathic symptoms
    - POSAS score ≥ 5 on question evaluating itchiness
    - POSAS score  $\geq$  5 on question evaluating pain

Exclusion Criteria:

- Initial burn injury was less than 1 year old
- History of chemical or electrical burn
- History of CO2 treatment to the scar of interest
- Genetic or acquired conditions that severely affect systemic wound healing or collagen formation (vasculitis, diabetes, Ehlers-Danlos syndrome, radiation therapy to the scar site or use of immunosuppressive medications within the last year, active cancer)

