For the procedure itself, 6mL of anticoagulant citrate dextrose A (ACD-A) will be drawn up in a 60mL syringe, after which 44 mL of the patient's own venous blood will be drawn into the same 60mL syringe using standard venipuncture techniques (Bellus Medical, 2019). While patient is waiting in the examination room, the sterile tubes of blood will be centrifuged by the ELMI CM-7S centrifuge which takes approximately 10-15 minutes. While waiting for the PRP to undergo centrifugation the scar to be treated will first be wiped with an alcohol swab, then measured and marked out with a marking pen such that the entirety of the scar will fit into a rectangle that is drawn, and the rectangle is filled entirely with the scar tissue. A ruler will be used to measure the scar in its greatest horizontal span, and the midway point will be marked with a vertical line. The length and height of the rectangle will be recorded. The vertical and horizontal distance from the nearest point-like anatomic landmark (e.g., xiphoid process) to the two edges of the rectangle will be documented so that the rectangle can be recreated at a later date. A photo of the outlined scar(s) will be obtained with a digital camera, with a ruler in view placed against the skin adjacent to the scar for reference as well as a "L" and "R" to designate laterality. The area inside the rectangle will then be subdivided with a marking pen into 1cm x 1cm square boxes, with the plan of injecting 1mL of either PRP or normal saline into each 1 square cm box.

The unblinded researcher who does not participate in the scar assessments will review the unblinded REDCAP containing the pre-designated treatment group (termed "Right and Left") and will inject the PRP and saline into the scar. The syringes will be covered with a white sticker and labeled such that the patient is unable to infer which syringe contains PRP (PRP is yellow

with a red hue and normal saline is clear). The unblinded researcher will then log this treatment into the unblinded REDCAP.

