# One Month Status-Post First Treatment (Day ~30):

At the one-month follow-up visit, the patient's treated scar will be identified with the assistance of old photos and measurements, and the rectangle will be re-marked out. The patient's blood will be collected in the same manner as Day 1 and spun down in the ELMI centrifuge. The patient and blinded providers will complete the VSS and POSAS while waiting, and the scar will then be marked into 1cm squares for subsequent treatment. The two different halves of the scar will be treated with the same substance that they were in the first round by the unblinded researcher.

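### In larger eligible scars, one fixed blood draw cannot supply PRP at 1 mL per cm², and the plan has neither a size cap nor a shortfall rule

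*Combined protocol and SAP*

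**What the plan says.** All references are to the combined protocol and SAP.

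- **Dose.** Section 6, Day 1, divides the marked rectangle into 1 cm squares, "with the plan of injecting 1mL of either PRP or normal saline into each 1 square cm box". A vertical line at the midpoint of the widest horizontal span separates the two halves.
- **Supply.** The same section puts 6 mL of ACD-A in a syringe, and "44 mL of the patient's own venous blood will be drawn into the same 60mL syringe". At one month, "blood will be collected in the same manner as Day 1 and spun down in the ELMI centrifuge". The visits at two, three and four months follow the one-month visit. No second draw is described.
- **Order.** "While waiting for the PRP to undergo centrifugation the scar to be treated will first be wiped with an alcohol swab, then measured". On Day 1 the blood has therefore been taken before the scar is measured.
- **Area.** "the entirety of the scar will fit into a rectangle that is drawn, and the rectangle is filled entirely with the scar tissue". The length and height are recorded, but no maximum is attached to them.
- **Eligibility.** Section 4 asks for a "Thermal burn scar on the trunk or abdomen", at least one year old and meeting a severity or symptom threshold. It sets no limit on size.
- **Masking.** The syringes are covered and "labeled such that the patient is unable to infer which syringe contains PRP".

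The visible text gives no expected PRP yield, no order in which boxes are filled, no rule for a shortfall and no matching of saline volume to the PRP available.

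**The concern.** The dose scales with scar area and the supply does not. Eligible scars can therefore be too large to treat as written, and the person injecting has to improvise, possibly differently at each of the five treatment sessions. Saline has no comparable limit, so a shortfall can fall on the PRP half alone.

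The strength of the design is that each patient supplies two halves meant to differ only in the substance injected. If boxes on the PRP side are left empty, that half is scored as a mixture of injected and uninjected scar, and the difference is diluted. If less is injected per box, the halves differ in volume as well as substance, and the direction of the resulting error is unknown. Covering the syringes does not hide a side that receives visibly fewer injections, and the patient rates part of the POSAS.

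**Working it through.** The plan states no yield, maximum area or total injected volume, so there is no figure of its own to reproduce. The check is a volume balance.

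**Inputs from the plan (section 6, Day 1):** 44 mL of blood, 6 mL of ACD-A, 1 mL per cm², half of the rectangle given PRP.

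**Input assumed:** haematocrit 0.36 to 0.50.

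**Need.** PRP needed (mL) = area (cm²) / 2 × 1 mL/cm². The largest rectangle that can be treated is therefore 2 × PRP volume.

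**Bound 1, the whole syringe.** 44 + 6 = 50 mL, so 2 × 50 = 100 cm². No haematocrit is needed. The bound is generous, since it counts the red cells as PRP.

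**Bound 2, all plasma plus all ACD-A.** Volume = 44 × (1 − haematocrit) + 6.

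| Haematocrit | Volume (mL) | Largest rectangle (cm²) | Side of square (cm) |
|---|---|---|---|
| 0.36 | 28.16 + 6 = 34.16 | 68.3 | 8.3 |
| 0.40 | 26.4 + 6 = 32.4 | 64.8 | 8.0 |
| 0.50 | 22.0 + 6 = 28.0 | 56.0 | 7.5 |

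**Practical limit.** The Background describes PRP as the platelet-rich layer only, so the real volume Y is below Bound 2. Y is not stated. By assumption: Y = 6 mL gives 12 cm², 10 mL gives 20 cm², and 15 mL gives 30 cm².

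**Illustrative rectangles (sizes chosen here, not taken from the plan):**

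- 8 × 6 cm = 48 cm² needs 24 mL. This is inside Bound 2, so whether it can be treated depends on Y. At Y = 15 mL the shortfall is 1 − 15/24 = 38%.
- 10 × 8 cm = 80 cm² needs 40 mL. Even all plasma plus ACD-A covers only 28/40 = 70% to 34.16/40 = 85%.
- 15 × 10 cm = 150 cm² needs 75 mL, which is more than the 50 mL in the syringe.

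**Whether the text escapes the bound.** The rectangle sentence can be read as enclosing the whole scar or as lying inside it. On the first reading the area is set by the scar, which section 4 does not limit. On the second it is set by the operator, and no size is given. Neither reading ties the area to the supply.

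**The case against.** The strongest objection is that no impact has been shown. The documents give no scar sizes, and if nearly all enrolled scars are small the gap hardly matters. That stands: the number of affected patients cannot be worked out.

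Several stronger readings are tempting, and the documents do not support them.

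- **A limit of 22 to 29 cm².** Section 3 describes a case report in which "platelet concentrations between 300% and 400% were applied to the edges of the burn". Read as 3 to 4 times baseline with perfect recovery, 44/4 = 11.0 mL and 44/3 = 14.7 mL would cover 22 to 29 cm². But this is another team's preparation in one patient, and the present protocol sets no enrichment target.
- **A stated loss of power.** Section 10 gives no effect size or power level, only that a cited study reached power with 31 patients. Any percentage would rest on a chosen baseline power, chosen scar sizes and a chosen fraction of patients affected.
- **A shortfall certain to be one-sided.** The plan does not say that saline continues at full volume when PRP runs out. An operator might match the halves unprompted. The imbalance is possible, not certain.
- **A biopsy taken from uninjected scar.** This needs boxes filled from one edge and less than half of the PRP side covered. Neither is stated.

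It is also fair to say that Day 1 cites a supplier reference, which may give a nominal yield and whose contents cannot be judged here. The unblinded researcher already records each treatment, although no volume is specified. Finally, a rectangle drawn inside the scar would let the operator limit the area. That helps only if a size is given.

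What survives is the conflict itself. Bound 1 uses only figures in the plan, and Bound 2 adds only a haematocrit.

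**Conclusion.** The concern holds as a conflict between stated dose and stated supply. For any rectangle above 100 cm² the dose is impossible whatever the preparation. Above about 56 to 68 cm² it would take more than all the plasma and anticoagulant, assuming haematocrit 0.50 to 0.36. The working limit is lower by an amount that depends on the unstated yield.

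In scars above the limit, the PRP half can receive less volume or fewer injected boxes than the saline half, with possible dilution, confounding by volume and loss of patient masking. Scars within supply are unaffected. The size of any effect on the result cannot be given. The change should be made because it is cheap and protects the within-patient contrast, not because a particular loss has been shown.

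**What to change.** Add to section 6, Day 1, and apply at each later treatment visit:

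1. **Cap the area.** Set a maximum treated rectangle of 2Y cm², where Y is the PRP volume in mL that the team expects from one draw (for example 20 cm² if Y is 10 mL). In a larger scar, mark one rectangle of that size after consent. Score its two halves before the first injection and at every later visit, and take the biopsies from those halves. Leave the section 4 eligibility scoring on the whole scar, in its present Day 1 order.
2. **Shortfall rule.** If PRP is still short at a session, spread it evenly over all boxes of the PRP half and inject the same mL of saline per box in the other half.
3. **Log volumes.** Record the mL of PRP and of saline injected in the unblinded REDCAP.

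**Cost.** A few sentences of protocol text, two values per session (2 × 5 sessions = 10 per patient), and in larger scars one extra baseline scoring of the marked halves, which fits in while the blood is spun. No extra blood, visits or patients are needed, and eligibility does not change. The real price is that in larger scars only a test area is treated, so results apply to that area and those patients do not have the whole scar treated.

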## Four Months Status-Post First Treatment (Day ~120):

The four-month follow-up visit will follow the same protocol as the one-month visit.

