This study is categorized as standard risk. Autologous platelet-rich plasma has been studied extensively and has been found to be extremely safe for human use, as it is derived from the patient's own body. The most severe side effects that have been observed from PRP treatment are erythema and swelling at the application site, which subsides within 1-3 days. All patients will receive a pre-screening survey to eliminate those who meet any of our exclusion criteria that may put them at any additional risk for complications. To decrease the chance of any injectionsite-related infection, all sites will be cleaned adequately, and all procedures will be performed using proper sterile technique. Because this is an injection, the possibility of infection or minor blood vessel or nerve damage exists, but these are essentially theoretical risks, as these complications have not been observed in any studies, we are aware of. Nevertheless, in the event of any PRP-related complication, patients will have access to a team member through the clinic phone number or www.myhealthatVanderbilt.com and will be evaluated promptly. Regarding the skin biopsy, sterile technique will be used to minimize the risk of infection, and proper biopsy site closure performed by qualified persons will minimize the risk of wound breakdown. Further, 2mm punch biopsy sites are at very low risk of wound breakdown given their small size. If an infection were to occur at this site, it would be promptly treated with appropriate antibiotics and wound care.

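### The patient is masked only by a sticker and label on the syringes, although the two fluids differ in colour and each half of the scar gets the same fluid at all five sessions; this can bias the patient POSAS, including pain and itch

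*Combined protocol and SAP*

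**What the plan says.** All references are to the combined protocol and SAP.

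- **Masking of the patient (section 6, Day 1).** "The syringes will be covered with a white sticker and labeled such that the patient is unable to infer which syringe contains PRP". The same sentence explains the need for this: PRP is yellow "with a red hue and normal saline is clear". No other patient-masking step is described.
- **Injection (section 6, Day 1).** The scar is divided into squares, "with the plan of injecting 1mL of either PRP or normal saline into each 1 square cm box".
- **Who injects (section 6, Day 1).** "The unblinded researcher who does not participate in the scar assessments will review the unblinded REDCAP" and injects both halves. Section 5 keeps the side allocation in a REDCap form that the scar evaluators cannot open.
- **Repetition (section 6, one-month visit).** "The two different halves of the scar will be treated with the same substance that they were in the first round". The two-, three- and four-month visits repeat this; for example, "The four-month follow-up visit will follow the same protocol as the one-month visit".
- **Scoring (section 6, one-month visit).** "The patient and blinded providers will complete the VSS and POSAS while waiting", that is, before that day's injection but after all earlier ones. On Day 1 the patient fills in one POSAS form in the waiting room, before the scar has been marked and halved.
- **Outcomes (section 2, Specific Aims).** Aim 1 uses the VSS and the POSAS. Aim 2 is neuropathic pain, with no separate instrument named. Section 4 lists the POSAS itch and pain questions under neuropathic symptoms.

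**The concern.** Saline is injected into the other half so that expectation acts equally on both. That works only while the patient does not know which half is which. The protocol names a colour difference and then hides it in one place, the syringe. The patient is awake (section 2 says PRP needs no anaesthesia), and the scar is on the trunk or abdomen, often within view. Both halves receive many small injections, with no screen, drape, hub cover or set injection order.

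Because the sides never change, the loss of the blind is permanent for that patient. A patient who knows the PRP half may rate it better through expectation alone. For pain and itch no other outcome in the plan could show this, because only the patient can score them. The plan also never asks which half the patient believes received PRP, so a failed blind would go unnoticed.

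**Working it through.** The plan gives no figure on masking to reproduce. The check is a comparison of the text, one count, and a test of whether the bias can be sized.

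**Step 1. What the sticker covers.** The stated hazard is the colour of the fluid. The stated protection covers the syringe. Fluid is also visible at the hub and wherever it leaks onto the skin, and nothing in section 6 covers those places. Colour is the only difference between the fluids that the protocol documents; visibility at the hub or on the skin is inferred from it.

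**Step 2. Sessions and scorings.** Treatment is given on Day 1 and about Days 30, 60, 90 and 120, which is 5 sessions, all on the same sides. Scoring precedes injection at each treatment visit, so sessions already received at each scoring are:

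| Scoring | Earlier sessions |
|---|---|
| Day 1 | 0 |
| Day ~30 | 1 |
| Day ~60 | 2 |
| Day ~90 | 3 |
| Day ~120 | 4 |
| Day ~150 | 5 |
| Day ~365 | 5 |

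Every post-baseline patient score follows at least one chance to identify the side.

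**Step 3. Which outcomes depend on the patient's blind.**

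| Outcome | Scored by | Depends on the patient's blind |
|---|---|---|
| VSS, observer POSAS | Blinded providers | Only if the patient tells them |
| Histology | Laboratory | No |
| Patient POSAS, scar items | Patient | Yes, with the rows above as a cross-check |
| Patient POSAS, pain and itch | Patient | Yes, with no cross-check |

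**Step 4. Can the bias be sized?** Let u be the share of patients who know the PRP side, and b the shift that knowledge causes in their between-half difference, in SDs of that difference. The mean bias is u × b. The documents give neither value, so what follows is illustration.

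*Share unmasked.* With a chance c per session of a revealing cue, u after five sessions is 1 − (1 − c)^5 if sessions are independent. If the same patients are always the ones exposed (scar site, line of sight), u stays at c.

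| c (assumed) | Same patients each time | Independent sessions |
|---|---|---|
| 5% | 5% | 1 − 0.95^5 = 23% |
| 10% | 10% | 1 − 0.90^5 = 41% |
| 20% | 20% | 1 − 0.80^5 = 67% |

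*False-positive rate.* Assume no true effect, a paired between-half comparison, n = 35 (section 10) and two-sided 0.05 (section 10 does not state sidedness). The rate is Φ(√35·u·b − 1.96) + Φ(−√35·u·b − 1.96).

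| u, b (assumed) | Normal approximation | Simulated Wilcoxon signed-rank |
|---|---|---|
| 0.25, 0.3 | 7.3% | 6.7% |
| 0.50, 0.3 | 14.4% | 13.2% |
| 0.50, 0.5 | 31.6% | 27.6% |
| 0.75, 0.5 | 60.2% | 53.7% |

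The answer runs from close to the nominal 5% to about 60%, depending wholly on assumed inputs. The documents establish an open route for bias, but not its size.

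**Step 5. Is a between-half patient score defined?** Bias between halves presupposes that the patient scores each half. Aim 1 compares PRP with saline on the POSAS, which requires it. Section 6 does not say so, and the single Day 1 form is completed before the halves exist. As written, there is no per-half patient baseline.

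**The case against.** The strongest reply is that the protocol already has a restricted allocation record, an injector who does not score, blinded raters and masked syringes, and that the rest is conjecture. Several parts of this stand.

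- **Only colour is documented.** A reader might take "erythema and swelling at the application site, which subsides within 1-3 days", said of PRP in the risk text, as a second cue. It is not shown to be one, because the text does not say that saline spares the skin. In the saline-controlled split-face laser study summarised in section 3, both sides had erythema and oedema, and both resolved sooner on the PRP side (6.1 against 7.1 days and 5.9 against 6.8 days). A difference in injection sensation has no support in the documents.
- **Accumulation is not established.** A reader might infer that 41% or 67% of patients would be unmasked, or that the bias would grow and imitate a cumulative benefit. Both need cues that are independent between sessions. If the same patients are exposed each time, the share stays flat.
- **There is a partial cross-check.** It would be too strong to say that nothing collected could reveal the bias. A patient-only benefit without support from raters or histology would be a warning for scar outcomes. It does not help with pain and itch.
- **Some scars may be out of sight.** The trunk may include the back.
- **Order alone reveals nothing** unless the patient learns which fluid goes first. Fixing it is a precaution that costs nothing.

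What does not stand is the suggestion that the existing safeguards cover the patient. They mainly protect the raters.

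**Conclusion.** The concern holds as a gap in patient masking that is cheap to close. The documents establish three facts: the protocol states a colour difference, a sticker and label are the only patient mask at injection, and the sides are fixed over five sessions. That leaves the patient POSAS open to expectation bias, most importantly on pain and itch, which are all that Aim 2 has. The likely direction is towards PRP, but this is a possibility that no data in the documents measure.

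No numerical size should be attached; the figures above only show how far the answer moves with the assumptions. The conclusion rests on fluid being visible outside the barrel, and on the patient POSAS being scored for each half, which the protocol needs but does not state. The consent pages were not available, so what patients are told about the two fluids was not checked. No defect in rater masking follows from this point.

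**What to change.** In section 6, Day 1, and by reference in the one- to four-month visits:

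1. **Screen the field.** Use a screen or drape so that the patient sees neither the syringes nor the scar from when the syringes are brought in until both halves have been wiped clean and covered identically.
2. **Fix the side order.** Inject in one order, for example left then right, in every patient and session, whatever the allocation. Because side is randomised, the order then carries no information about treatment.
3. **Define the patient score.** State that the patient POSAS is completed separately for each half, including a baseline taken after the scar is divided.

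Optionally, ask the patient right after session 1 which half they think received PRP. Log the answer in the unblinded REDCap or another form the raters cannot open, since the blinded form holds the VSS and POSAS scores and could pass the patient's belief to them. Report it descriptively. If all 35 patients answer, 24 or more correct would be unlikely by chance (exact one-sided p = 0.020), and a true correct rate of 75% would reach that count with probability 86%. Late guesses partly reflect efficacy and should not be used to split the treatment effect.

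The cost is a drape and coverings, a few minutes per session, a second patient POSAS form at each scoring, and one form item. Sample size and schedule do not change. The session 1 guess cannot be recovered later, so the wording should be settled before patients are treated.
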